# vi. ROLES AND RESPONSIBILITIES OF TRIAL MANAGEMENT COMMITEES/GROUPS & INDIVIDUALS

## **Trial Management Committees**

Trial Steering Committee (TSC) has the role/responsibilities of providing overall supervision of the trial concentrating on the trial's progress, including adherence to the approved protocol, subject safety, and consideration for new information. This group will monitor the on-going relevance and need for the trial in view of published literature and be responsible for the on-going compliance to ethical and regulatory standards. The rights, safety and well-being of the participants are the most important considerations and will prevail over the interests of science and society. York Trials Unit (YTU) is responsible for maintaining the TSC documentation during the course of the trial to ensure compliance with the Trial Master File (TMF). The TSC must have a majority independent representation and include the Chair. The TSC must meet regularly and send reports to the sponsor and funder. The TSC will agree proposals for substantial protocol amendments and provide advice to the sponsor and funder regarding approvals of such amendments. The TSC will provide advice to

the investigators on all aspects of the trial/project. Lay members or patient representatives are included. Independent members must make up a minimum of 75% of the TSC membership.

- The Data Monitoring and Ethics Committee (DMEC) will be a committee of independent experts external to the study assessing the progress, safety data and critical efficacy endpoints of the study. The DMEC will also review essential parts of study conduct e.g., protocol adherence and patient withdrawal. In order to do this the DMEC will review unblinded study information (on a patient level and treatment group level) during the conduct of the study. Based on its review the DMEC will provide the TSC, sponsor and funder with recommendations regarding study modification, continuation or termination. Independence is a key characteristic of the DMEC, and committee members will be completely uninvolved in the running of the trial and not be in a position to be unfairly influenced (either directly or indirectly) by people, or institutions, involved in the trial. The implementation of DMEC recommendations will be the responsibility of the TMG and sponsor. The DMEC will include a clinician with expertise in the field, a biostatistician and a person able to consider ethical aspects.
- The TMG will meet regularly to ensure all practical aspects of the trial are progressing well and working well and everyone within the trial understands them. The TMG will be made up of chief investigators (Cl's) and co-applicants, with others with necessary expertise invited to join as needed.
- End Point Committee: [name], [name] and [name] will form a blinded end-point committee for review of outcomes outside LTHT. A separate committee will be for to review outcomes for patients within LTHT including [name], [name] and [name]. Clinicians from outside the TMG will be trained to take on these roles during the trial.

## ix. TRIAL FLOW CHART

The EXTEND Trial protocol ISRCTN no. 72819021

#### 1 BACKGROUND

Introduction: The management of complicated intra-abdominal infection (cIAI) is one of the main infection challenges in surgical patients. Complication rates are high and uncertainty over the optimal antibiotic strategy remains [1]. cIAIs extend beyond a hollow viscus (an organ with a lumen such as the bowel) in the abdomen into the peritoneal cavity and are associated with either abscess formation or peritonitis. cIAIs are the second commonest cause of sepsis in patients on intensive care units (ICUs) and cause significant morbidity and mortality [2,3]. Current treatment approaches for cIAI fail to prevent complications, including death, cIAI relapse requiring additional source control procedures and extra-abdominal infections (wound infections, urinary tract infections and respiratory tract infections). Sepsis, which can result from cIAI relapse and extra-abdominal infections, causes longer term functional, cognitive and mental health impairments [4]. cIAIs are heterogeneous in aetiology and include spontaneous infections from a perforated intra-abdominal viscus, and post-operative infections. However, cIAIs have a common disease process which is bacterial infection of the peritoneal space. Hence, all cIAIs are managed with surgical or radiological source control (e.g., resection of damaged bowel), plus antibiotic therapy. There are uncertainties about the duration of antibiotic therapy that best prevents relapse and prevents extra-abdominal infections in patients with cIAI. A national audit of cIAI management in the UK showed there is variation in antibiotic treatment strategies, and there remains no UK guidance on the management of cIAIs [5.6]. However, for serious infections outside the abdomen with a high treatment failure rate (e.g., brain abscess, lung abscess, mastoiditis, septic arthritis, osteomyelitis, and prostatitis), microbiologists often give at least 28-days of antibiotic therapy [7]. The effectiveness of a fixed-extended-duration strategy of 28-days in UK patients with cIAI is unknown, having only been studied in a feasibility trial, leaving an evidence gap for the NHS [8]. We will investigate whether such a treatment strategy improves the longer-term outcomes for these patients; and determine whether this approach is likely to be an efficient use of NHS resources. This proposal aims to investigate the clinical and cost-effectiveness of an unproven approach to patient management in comparison to standard care within the NHS.

**Review of existing evidence:** Systematic reviews of the evidence have been completed by the Surgical Infection Society (SIS 2017) and Chinese Society of Surgical Infection (CSIS 2020) [9,10]. The SIS encourages a 4-day antibiotic duration as a treatment for cIAI. However, this strategy is difficult for clinicians to adhere to, as demonstrated by the STOP-IT trial where 18% of patients randomised to a 4-day treatment strategy received more than the allocated 4 days of treatment (receiving a median of 11 days). In addition, a UK cIAI audit found a median antibiotic duration of 12 days (IQR 7-18 days). We therefore excluded a 4-day duration of antibiotics as a standard treatment comparator. The CSIS recommend up to 10 days antibiotics for severe cIAI. Guidance from the World Society of Emergency Surgery on cIAI recommends shorter durations of antibiotics should be

prescribed where possible, but clinician judgement and inflammatory blood markers should be used in determining a treatment end date [11].

There are three published RCTs of antibiotic durations for cIAI; STOP-IT, DURAPOP and a cIAI feasibility trial [8, 12,13]. These trials all compared different antibiotic durations and together provide a signal of efficacy for longer antibiotic treatment durations. STOP-IT reported that a median of 4 days antibiotics was as effective as a median of 8 days, with surgical-site infection, recurrent intraabdominal infection, or death occurring in 21.8% as compared with 22.3% respectively (p=0.92). However, despite the limited difference in treatment durations, the longer antibiotic durations significantly delayed time until relapse (p=<0.001), which is consistent with an incompletely treated infection. DURAPOP assessed antibiotic durations for ICU patients with cIAI and compared 8 to 15 days of antibiotics. DURAPOPs secondary outcomes reported a significantly lower rate of radiological drainage in patients treated with 15 vs. 8 days antibiotics (9%, 11/116 vs. 19%, 23/120, p=0.04). Other outcomes signalled a 15-day treatment strategy may have benefits including: median length of ICU stay (12 days vs.13 day, p=0.14), rate of bacteraemia (4% vs.11%, p=0.059) and rate of microbiological failure (16% vs. 23%, p=0.13). The cIAI feasibility trial was a 30 patient RCT conducted in Leeds, UK, and designed after consultation with a Leeds Cancer-Patient and Public Involvement (LC-PPI) group [8]. It compared 28-days antibiotics to ≤10 days for patients with cIAI. It found a relapse rate of 4/17 (24%) in the ≤10-day arm, vs. 0/13 (0%) in the 28-day arm. Infections outside the abdominal cavity were diagnosed in 6/17 (35.3%) of those in the  $\leq 10$ -day arm, vs. 1/13(7.9%) in those treated for 28-days. Current UK practice and outcomes in patients with cIAI is described by a 417-patient observational study across 30 UK hospitals [5]. In the 17.3% of patients with relapse the median time until relapse was 18 days (IQR: 13-30 days); in the 11.3% of people who died the median time to death was 23 days (IQR: 12-51 days). Antibiotic treatment had a median duration of 12 days (IQR 7-18 days). The rate of adverse events in patients treated for cIAI varies by the patients group studied. Mortality rates have been reported at up to 50% in at risk populations with severe illness, and at 10 to 20% in studies from more broad populations of patients. The need for additional source control procedures, rate of relapses and rate of treatment failure likewise varies by population and definition, being reported in 20 to 60% of patients [2,3,15-19].

#### 2 RATIONALE

The cIAI feasibility trial and a survey of clinicians showed there is equipoise with regards to this issue and a desire to see good evidence on this. Our UK data suggests that current practice results in unacceptably high rates of cIAI relapse and extra-abdominal infection. As a guiding rule, shorter antibiotic durations are important to combat antimicrobial resistance, but this is not true when these shorter courses need repeating and result in more days in hospital. Optimal care for patients should be our primary concern. The impact of the proposed EXTEND trial, which is studying fixed-extendedduration antibiotics in patients with complicated intra-abdominal infection, will be to improve patient outcomes by providing clinicians with reliable evidence to support them in making the best treatment choices for their patients. If the longer duration strategy is more effective than standard treatment, it is likely to offer direct benefits to the NHS in terms of costs. The literature supports this as when efficacy of antibiotic therapy for cIAI increases, cost savings have been demonstrated. Cost savings included shorter hospital stays and an increase in Quality Adjusted Life Years (QALYs) [20,21]. Reductions in cIAI relapse will also reduce the use of radiological and surgical NHS resources.

## 2.1 Assessment and management of risk

This trial is a non-CTIMP (Clinical Trial of Investigational Medicinal Product) trial being a trial of treatment duration strategy, as opposed to a trial of an IMP. Participation in the trial is not known to offer risks to participants that are overall higher or lower than the risk of standard medical care.

## 3 OBJECTIVES AND OUTCOME MEASURES/ENDPOINTS

## Objectives

## 3.1 Primary objective

• To complete a multicentre, open label, two-arm, parallel group, pragmatic, randomised controlled trial with internal pilot to determine if a fixed-extended-duration of 28-days antibiotic treatment is superior to standard care based on clinical outcomes and quality of life assessed over six months of follow up.

## 3.2 Secondary objectives

- To conduct a detailed economic evaluation to assess the cost-effectiveness of these comparisons at the end of the treatment phase and throughout the life of the patients.
- To assess, by means of a study within a trial (SWAT), the effect on trial recruitment of a picture story book patient information resource.

## 3.3 Outcome measures/endpoints

We have designed the trial such that the majority of data can be collected electronically from routinely generated data e.g., routine observations, blood tests and prescription charts. This allows data collection to be streamlined and efficient for research staff.

## 3.4 Primary endpoint/outcome

The primary outcome measure is: Treatment failure within 180 days of randomisation.

For in-patients, treatment failure is defined when a patient meets objective criteria for both inflammation and infection within a 5-day period. Meeting of the criteria for inflammation may precede or follow the date that criteria for infection were met (the first day of an eligible antibiotic treatment course). These criteria are:

Criteria for Inflammation

- A fever (≥ 37.8 degrees Celsius) or hypothermia (≤36 degrees Celsius), plus
- A neutrophilia (>7.5 x10^9/L) or neutropaenia (<1.8 x10^9/L), plus
- A CRP over 100 mg/L

#### PLUS, criteria for infection

- Initiation of a new antibiotic treatment course of  $\geq$  5 days, or
- A change in antibiotic treatment continued for  $\geq$  5 days, or
- Initiation of a new antibiotic treatment, or a change in antibiotic treatment, and death within 5 days, or
- Bacteraemia with a recognised intestinal pathogen.

New or changed antibiotic treatments must not be antibiotic prophylaxis, a change to achieve oral administration from intravenous antibiotics only, a change to reduce the spectrum of activity (targeted antibiotic treatment) or made due to antibiotic allergy only. New/changed antibiotics can include additional antibiotics, added to an ongoing treatment regimen. The first day of an eligible new/changed antibiotic treatment is called the antibiotic reference date. Inflammation 5 days either side of this antibiotic reference date can be assessed against the criteria for inflammation. A blinded endpoint committee will assess and classify data including but not limited to inflammation and antibiotic treatments to assign participants with treatment failure.

Once discharged, treatment failure requires re-admission to hospital and the in-patient criteria above to be met. Alternatively, they must have been admitted to hospital and have consumed antibiotics for > 48 hours prior to admission. Treatment failure cannot be assigned based on inflammation (fever, neutrophilia and CRP>100mg/L) detected within the 5 days after an operative procedure (surgical or radiological). Treatment failure can be assigned based on pre-operative inflammation and post-operative antibiotic changes. Treatment failure cannot be assigned due to evidence of inflammation or infection, as defined above, within the first 5 days of antibiotic treatment for the initial cIAI. If treatment

is extended beyond the intervention duration this should be considered a new antibiotic treatment course.

Treatment failure measurement: A patient's temperature is measured as part of routine clinical care two to four times daily and recorded in their medical records when in hospital. Patients have the neutrophil count and CRP measured, by means of a blood test, when admitted to hospital, or when an infection is suspected. It will be required that these blood tests are completed within 3 days of an antibiotic prescription and monitored every 72 hours while receiving antibiotic therapy until there has been a reduction in CRP concentration of ≥25%, as per standard clinical practice. Patients' medication charts will be assessed to identify new or changed antibiotic consumption. A blinded endpoint committee will review evidence of inflammation plus antibiotic consumption, in combination with documented antibiotic allergies and microbiology reports, from the preceding two weeks. This review will determine if antibiotic consumption is a new or change in antibiotic treatment, and not prophylaxis, a change made to achieve a narrowing of spectrum, an oral switch only or made due to allergy only. The DMEC will audit the blinded endpoint committee and the audit will be reviewed within the internal pilot.

Intestinal pathogens include: Anaerobes (e.g., Bacteroides), Enterobacterales (e.g., Citrobacter, E.coli, Enterobacter, Klebsiella, Serratia), Enterococcus spp., Pseudomonas spp. and Streptococcus species.

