#### 8.1 Intervention

A fixed-extended-antibiotic duration of 28-days effective therapy for patients with cIAI. Effective antibiotic therapy is defined as therapy likely to be active against common pathogens causing cIAI and not limited by proven antimicrobial resistance detected pre-randomisation according to standard laboratory criteria.

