#### 8.4 Assessment of adherence with treatment

Monitoring adherence to antibiotics prescribed while an in-patient will be carried out by monitoring patient's prescription charts. An amount of antibiotics prescribed orally may be consumed while an out-patient. We recognise the importance of adherence to ensure separation between the trial arms in terms of the intervention durations. We therefore need to review outpatient adherence within our internal pilot. We will do this by means of a modified Brief Adherence Rating Scale [25] in the 1-month participant questionnaire. There will be no process of formally assessing if antibiotic treatment is adherent to the protocol in those treated with standard care antibiotic treatment. In participants receiving a fixed extended-duration antibiotic treatment of 28 days, this will be considered protocol adherent where the overall treatment duration is within 5 days of this duration.

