## 10 STATISTICS AND DATA ANALYSIS

## 10.1 Sample size calculation

The primary outcome for this study is treatment failure. Using an estimated proportion of treatment failure in the standard treatment group of  $\geq$  50% over the 180 days of follow up, an effective sample size of 1048 patients (524 per arm) obtains 90% power to detect a 10% (absolute) reduction in incidence of the clinical outcome in a two-sided test of size 5%. Assuming 10% attrition 1166 patients (583 per arm) are required. The sample size calculation was carried out using Stata version 16.0.

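### The alternative post-discharge route to treatment failure does not exclude the allocated course, so it can count 28-day patients re-admitted while on that course as failures

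*Protocol*

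**What the plan says.** Protocol section 3.4 sets the endpoint: "The primary outcome measure is: Treatment failure within 180 days of randomisation". For in-patients, failure needs inflammation (temperature, neutrophils and CRP) plus evidence of infection, the latter mainly a new or changed antibiotic treatment. Prophylaxis, oral switch, narrowing of spectrum and changes for allergy are excluded.

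After discharge there are two routes. The first is re-admission with the in-patient criteria met. The second reads: "Alternatively, they must have been admitted to hospital and have consumed antibiotics for > 48 hours prior to admission". That sentence mentions no inflammation, no reason for admission, no new or changed treatment, and no exception for the course the patient was randomised to receive.

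Section 8.1 defines the intervention: "A fixed-extended-antibiotic duration of 28-days effective therapy for patients with cIAI". Section 8.4 expects part of it to be taken at home: "An amount of antibiotics prescribed orally may be consumed while an out-patient".

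Section 3.4 also says that a blinded endpoint committee assigns failure, and that its review decides whether antibiotic consumption is new or changed. It says that treatment continued past the intervention duration is a new course. It does not say whether these rules govern the second post-discharge route.

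**The concern.** Being on antibiotics for more than 48 hours before a re-admission is, in the 28-day arm, partly a consequence of allocation. If the allocated course can satisfy the second route, two patients with the same re-admission in, say, the third week can be classified differently only because one was still on the assigned course and the other had stopped.

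That would add failures preferentially to the intervention arm. In a superiority trial it would shrink a real benefit, and with enough conversions it could look like harm. The better the arms separate in duration (the pilot's green threshold in section 4.1 is more than 10 days), the more unequal the exposure. The same classification feeds DOOR, time to failure and number of failure episodes (section 10.2.4), and relapse, which is asked only of patients with a failure episode (section 3.6).

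**Working it through.** **1. What the second route can mean.** If it still required all the in-patient criteria, it would repeat the first route, so it must relax something.

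- Literal reading: admission plus more than 48 hours of antibiotics is enough. A 28-day patient re-admitted on the allocated course meets it.
- Milder reading: inflammation is still needed, and the 48 hours of antibiotics replaces the infection criterion. The allocated course then supplies that criterion, so a 28-day patient re-admitted with inflammation from any cause can fail without a new or changed antibiotic.

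Under both readings the allocated course can help to trigger the endpoint.

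**2. Exposure by arm.** The intervention lasts 28 days. Section 1 (UK observational study) gives a median of 12 days, IQR 7-18. The difference is 28 − 12 = 16 days at the median, and 28 − 18 = 10 to 28 − 7 = 21 days across the IQR, less whatever is spent in hospital.

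**3. The plan's own figure.** Section 10.1: "an effective sample size of 1048 patients (524 per arm) obtains 90% power to detect a 10% (absolute) reduction in incidence", two-sided 5%, control rate at least 50%; "Assuming 10% attrition 1166 patients (583 per arm) are required". With p1 = 0.50, p2 = 0.40, mean 0.45:

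n = [1.960·√(2·0.45·0.55) + 1.2816·√(0.50·0.50 + 0.40·0.60)]² / 0.10² = 519 per arm, against 524 stated (within 3%). Power at 524 per arm is 90.3%. Attrition: 524/0.9 gives 583 per arm, 1166 in total. The sample size reproduces and is not in dispute.

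**4. Effect of conversions.** Let q and r be the shares of true non-failures turned into failures by the second route in the 28-day and standard arms. Then:

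p_int = 0.40 + 0.60q, p_ctrl = 0.50 + 0.50r

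Power = Φ{[d·√524 − 1.960·√(2·p̄·(1 − p̄))] / √(p_ctrl(1 − p_ctrl) + p_int(1 − p_int))}, with d = p_ctrl − p_int and p̄ their mean.

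Example, q = 5%, r = 2%: p_int = 0.43, p_ctrl = 0.51, d = 0.08, power 73.8%.

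| q | r | Control | 28-day | Difference (points) | Power |
|---|---|---|---|---|---|
| 0% | 0% | 50.0% | 40.0% | 10.0 | 90.3% |
| 2% | 0% | 50.0% | 41.2% | 8.8 | 81.7% |
| 2% | 2% | 51.0% | 41.2% | 9.8 | 89.0% |
| 5% | 0% | 50.0% | 43.0% | 7.0 | 62.3% |
| 5% | 2% | 51.0% | 43.0% | 8.0 | 73.8% |
| 5% | 5% | 52.5% | 43.0% | 9.5 | 86.9% |
| 10% | 0% | 50.0% | 46.0% | 4.0 | 25.3% |
| 10% | 2% | 51.0% | 46.0% | 5.0 | 36.7% |
| 10% | 5% | 52.5% | 46.0% | 6.5 | 55.8% |

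In patients, q = 5% is 0.05 × 0.60 × 524, about 16 in the intervention arm. The protocol gives no rate of re-admission on treatment, so q and r are assumptions.

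**The case against.** A reader might infer that every re-admission after 48 hours of antibiotics counts, that 28-day patients fail automatically, and that the added failures fall almost only in their arm. The document does not support these stronger readings.

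- The sentence is phrased as something patients must satisfy, so it can be read as a necessary condition rather than a sufficient one.
- A blinded committee assigns failure, and its review of new or changed treatment is not expressly limited to in-patients. It may see an unbroken prescription and discount it.
- Calling only treatment beyond the intervention duration a new course suggests that the course within it is not new. DOOR in section 3.5 ties sepsis and death to antibiotics starting or changing, which presumes that a failure has such a date.
- Read literally, the route catches both arms for all 180 days. A quarter of patients in the UK study had 18 days or more of antibiotics, and later community courses for relapse or other infection would also count.
- Patients re-admitted early may be enriched for genuine failure, so true conversion could be small. Power figures with no control conversion are the unfavourable end.

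These points rule out the words automatic and almost only, and they rule out treating any single power figure as a prediction. They do not remove the problem. The new-or-changed rule is not linked to this route, and the route does not ask whether a course is new. The committee looks back two weeks, so the start of a 28-day course can lie outside its window, and being blinded it is not told which course is the allocated one. Under section 3.6, community prescriptions are captured where available and supplemented by self-report.

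**Conclusion.** The point holds in this form: as written, the alternative post-discharge route can count 28-day patients re-admitted on their allocated course as treatment failures, over a longer window than standard-care patients, and the bias runs against the intervention. The surrounding committee rules may limit this, but the protocol does not make them apply.

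The size cannot be derived from the document. If 2-10% of intervention non-failures and 0-5% of control non-failures were converted, with the control share no larger than the intervention share, the planned 10-point difference would fall to between 4.0 and 9.8 points, and power from 90.3% to between about 25% and 89%. This assumes the planning rates of 50% v 40%, 524 analysed per arm and a simple two-proportion test. The low end needs 10% conversion in one arm and none in the other, for which the protocol offers no evidence. The document also does not show that any case has been classified on the literal reading. The rule still needs correcting, because it lets the randomised treatment contribute to the definition of the primary endpoint in an open-label superiority trial.

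**What to change.** Reconcile the sentence with the rest of section 3.4.

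- State that the more than 48 hours of pre-admission antibiotics must be a new or changed treatment, subject to the exclusions already listed there (prophylaxis, oral switch, narrowing, allergy).
- State that continuation of the initial cIAI course, including the allocated 28-day course, does not count towards this route in either arm.
- State which inflammation evidence applies, using data available at re-admission. Requiring it within 5 days of a community start date would not work well: the measurements may not exist for a course begun earlier at home, and the route would nearly collapse into the first one.
- Put the same wording in the endpoint committee's instructions, and re-check any cases already classified under this route, blind to allocation.

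The cost is a short amendment to section 3.4, matching committee instructions, and a small amount of re-adjudication.

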## 8.2 Detailed specification of the intervention

The intervention is a strategy of a fixed-extended-duration antibiotic treatment of 28-days. The start of antibiotic therapy is the first day of effective therapy for cIAI treatment, which will generally occur before randomisation, but could be following randomisation if antibiotics given prior to randomisation are ineffective/inactive. The start date of antibiotic treatment will be determined by the patient's clinical team or clinical research team. Examples of antibiotic therapy that are not therapy for cIAI include antibiotic prophylaxis, or treatment for other infections e.g., cystitis. All treatment will be considered effective unless:

1) Antimicrobial resistance is identified on clinical samples collected before randomisation and that resistance is believed to be clinically relevant i.e., antibiotic treatment is changed based on the microbiological evidence of antibiotic resistance. The start date of fixed-extended-duration antibiotic treatment of 28-days will be re-set to day 0 where antibiotic treatment is changed based on pre-randomisation detection of antibiotic resistance. This strategy relates to the fixed-extended-duration treatment only, and the date of randomisation is not changed.

2) Antibiotics are prescribed for prophylaxis e.g., penicillin for splenectomy, elective surgery antibiotic prophylaxis, UTI prophylaxis

3) Antibiotics are prescribed for the treatment for other infections e.g., cystitis, and not effective against cIAI.

4) Antibiotics are oral antibiotics prescribed prior to hospitalisation

5) Antibiotics from a previous course of antibiotics, a previous course is one stopped for 48 hours or more.

The choice of antibiotic and route of administration are therefore selected by the treating clinician. Source control procedures (surgical and radiological) will be carried out as per standard practice.

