#### 8.3 Comparator

Standard care antibiotic duration. We describe standard care as being based on clinician judgment. Clinicians use the clinical progress of the patient in combination with inflammatory blood markers, surgical and radiological findings to guide standard treatment antibiotic durations. Treatment durations are not pre-determined or fixed in duration. Standard care antibiotic durations do not dictate the choice or route of antibiotics; as per the intervention arm standard care refers to antibiotic durations only. Source control procedures (surgical and radiological) will be carried out as per standard practice. The start of antibiotic therapy is the first day of effective therapy. When antimicrobial resistance is identified and believed to be clinically relevant i.e., antibiotic treatment is changed based on microbiological results, the start of antibiotic therapy will be re-set to day 0 if this occurs within the first 10 days of treatment. The end date for standard antibiotic duration is defined by the first 48-hour period without antibiotic therapy. The end date is the first date within this 48-hour period.

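### The primary endpoint's extension rule has a cut-off only in the 28-day arm, so identical continued treatment can be scored differently by arm and a blinded committee cannot apply it

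*Protocol*

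**What the plan says.** Section 3.4 of the protocol sets the endpoint: "The primary outcome measure is: Treatment failure within 180 days of randomisation". Failure needs all three inflammation criteria plus one of four infection criteria: a new antibiotic course of at least 5 days, a change continued for at least 5 days, a new or changed antibiotic with death within 5 days, or bacteraemia with an intestinal pathogen. Antibiotics added to an ongoing regimen count as new or changed. The section then adds that if treatment "is extended beyond the intervention duration this should be considered a new antibiotic treatment course". It does not define that duration. A blinded committee assigns failure.

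Section 8.2 fixes the intervention at 28 days. Section 8.3 says of standard care: "Treatment durations are not pre-determined or fixed in duration". Its end date is found only in retrospect, as the start of the first 48 hours without antibiotics.

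Section 1 cites a UK observational study with a median antibiotic duration of 12 days (IQR 7-18). On relapse it says: "In the 17.3% of patients with relapse the median time until relapse was 18 days (IQR: 13-30 days").

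**The concern.** An endpoint in an open-label trial must give the same answer for the same clinical course in either arm. Here one route to failure, extension of the current course, has a threshold in one arm and none in the other. A committee that follows the sentence as written must first learn the allocation, which defeats its blinding.

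Allocation also decides whether a patient is on antibiotics when a relapse occurs. Three of the four infection criteria depend on an antibiotic start or change. A patient who has stopped and restarts is scored; a patient drained while the same drug continues is not.

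The first asymmetry adds failures to the 28-day arm and the second removes some. Both act on the primary comparison. Time to failure, number of episodes and the DOOR use the same definition, and relapse is asked about only in patients with an episode of failure, so these outcomes inherit the problem.

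**Working it through.** **1. The same event in each arm** (inflammation criteria met in the window)

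| Event | 28-day arm | Standard care |
|---|---|---|
| Same regimen continued 5 or more days past day 28 | New course: failure | Still the original course: not scored |
| Change or add-on for 5 or more days | Failure | Failure |
| Bacteraemia, intestinal pathogen | Failure | Failure |
| Restart for 5 or more days after stopping | Failure | Failure |
| Drained in hospital while the same drug continues, before day 28 | Not scored | Not scored if still on antibiotics; if already stopped, a restart is scored |

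The first row is a direct difference in the rule. In the last row the rule is the same, but the arms differ in how often patients are in that state.

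**2. The plan's sample size.** Section 10.1 takes an "estimated proportion of treatment failure in the standard treatment group of" at least 50%, a 10-point reduction, two-sided 5% and 90% power. Per arm:

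n = [1.960·√(2·0.45·0.55) + 1.282·√(0.5·0.5 + 0.4·0.6)]² / 0.10² = 519.

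The log-odds-ratio form gives 522. The plan states 524, at which power is 90.3%. Attrition: 524/0.9 = 582.2, so 583 per arm and 1166 in all. The plan's figure reproduces.

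**3. Illustration: unscored relapses in the 28-day arm, no true effect.**
- Log-normal relapse time with median 18: σ = ln(30/13)/1.349 = 0.620.
- F(12) = Φ(ln(12/18)/0.620) = Φ(−0.654) = 0.257.
- F(28) = Φ(ln(28/18)/0.620) = Φ(0.713) = 0.762.
- Share of relapses between days 12 and 28: 0.762 − 0.257 = 0.505. As a share of patients: 0.505 × 17.3% = 8.7%.
- If a share f of these goes unscored, the observed rates are p₁ = 50% and p₂ = 50% − f × 8.7%.
- Chance of declaring benefit = Φ((p₁ − p₂ − 1.960·se₀)/se₁), with se₀ = √(2p̄(1−p̄)/524), p̄ the mean of p₁ and p₂, and se₁ = √((p₁(1−p₁) + p₂(1−p₂))/524). The total adds the small opposite tail.

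| f (assumed) | Shift, points | Rejection rate (nominal 5%) |
|---|---|---|
| 5% | 0.4 | 5.2% |
| 10% | 0.9 | 5.9% |
| 25% | 2.2 | 10.9% |
| 50% | 4.4 | 29.4% |
| 75% | 6.6 | 56.7% |

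Day 12 is only the median stopping day. Letting control duration vary log-normally (median 12, σ = ln(18/7)/1.349 = 0.700), independent of relapse time, puts about 44% of relapses in the gap, or 0.44 × 17.3% = 7.6% of patients. At f = 25% the shift is then 1.9 points and the rejection rate 9.5%.

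**4. Illustration in the other direction.** Take a true 50% v 40% and let the extension rule add failures to the 28-day arm only. By the same formula, power falls from 90.3% to 83.4% (+1 point), 73.9% (+2) or 62.3% (+3). These additions are also assumptions.

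**The case against.** Most relapses should score alike. Section 3.6 itself says that antibiotics are often escalated to a carbapenem when standard treatment fails; that is a change, and it counts in both arms if continued for 5 days. This argues for a small f, where the effect is slight. The illustration also assumes that every relapse in the cited study would meet all three inflammation criteria and that its times run from the start of antibiotics, which the protocol does not state. For discharged patients, section 3.4 has a loosely worded alternative based on more than 48 hours of antibiotics before admission. Read literally, it could score a patient on an unchanged regimen. All of this stands, and it limits the second asymmetry.

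It does not rescue the extension sentence. Section 8.4 speaks of intervention durations for both arms, so the term may have been meant for either. But a standard-care course has no planned end, and its end is defined as the moment antibiotics stop. Treatment cannot run past that point except as a restart.

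Three stronger readings are tempting but unsupported:
- That prolonged treatment can never be a failure in standard care. It can, through a change, add-on, restart or bacteraemia. Nor is extension alone a failure in the 28-day arm; inflammation and 5 days are also needed.
- That a significant result could not be put down to fewer infections. Source control procedures, complications and mortality are analysed by arm without the antibiotic-change rule.
- That the 5-day exclusion at the start of treatment runs on different clocks by arm. Section 8.2 says the start date "will be re-set to day 0 where antibiotic treatment is changed based on pre-randomisation detection of antibiotic resistance"; section 8.3 says "the start of antibiotic therapy will be re-set to day 0 if this occurs within the first 10 days of treatment". The exclusion, however, is tied to antibiotic treatment for the initial infection, and nothing links it to either reset.

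**Conclusion.** The extension sentence is defective as written. It scores the same continued treatment, with the same inflammation, differently by arm, and the blinded committee needs the allocation to apply it. This follows from the text of sections 3.4, 8.2 and 8.3 and needs no assumption.

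The restart-versus-continue asymmetry is real but confined to non-bacteraemic events managed without an antibiotic change. Its illustrated effect runs from negligible (5.9% rejection at f = 10%) to serious (29.4% at f = 50%), and f has no source in the protocol. The two asymmetries pull in opposite directions, so neither the size nor the sign of the net bias can be derived. The sample size is sound on its own inputs.

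**What to change.** (a) Replace the extension sentence in section 3.4 with one scoring rule that applies to every participant from a common time origin, whatever the allocation, so that the committee can apply it blind. The cut-off is for the sponsor to choose. It is a scoring rule only and changes no treatment. Reconcile section 3.4 with 8.2 and 8.3 and carry the wording into the committee's working instructions.

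(b) Pre-specify two sensitivity analyses of the primary outcome:
- (i) exclude failures assigned only through the extension rule;
- (ii) let the infection criterion also be met, alongside inflammation, by an unplanned post-randomisation source control procedure or by death, without an antibiotic change. Planned closure of an open abdomen, which section 3.6 counts as a separate procedure, should be left out.

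Source control procedures and deaths are already collected. The cost is a wording amendment and a little extra analysis. The downside is that a few standard-care patients on long courses may become failures. The change should be made before any outcome data are reviewed by arm.
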